7.3 Analysis of Adverse Events

All adverse events will be summarized by showing the number and percent of subjects which report the event. Events will also be reported by relationship to the procedure or device. Adverse events judged as probably or definitely related to the Indigo® Aspiration System will be analyzed as device-related; events judged as probably or definitely related to the Index Procedure will be analyzed as procedure-related. The IMR data will supersede the Investigator-reported data in all analyses of adverse events.

All serious and non-serious adverse events will be coded using the MedDRA dictionary. The number and percentage of subjects with AEs and SAEs, and all events leading to death (cause of death) will be summarized by body system and preferred term. Each subject will be counted only once within a category. Additionally, non-serious AE will be summarized for events that are reported by at least one (1) percent of the subjects.

8 Subgroup Analysis

To evaluate the impact of baseline condition on outcomes, subgroup analyses will be performed for the primary endpoints and secondary safety variables (listed in Section 1). The subgroups below will be used for these analyses:

- Age: < 65 years, \geq 65 years
- Gender: Male, Female
- Race: American Indian or Alaska Native, Asian, Black or African American, Native Hawaiian or Other Pacific Islander, Unknown or Not Reported
- Ethnicity: Hispanic or Latino, Not Hispanic or Latino, Unknown or Not Reported
- Baseline NYHA: Class I and II, Class III and IV
- Index event diagnosis: STEMI, NSTEMI

Descriptive statistics will be presented for each subgroup. The subgroup analysis will be conducted using Fisher's exact test, Wilcoxon rank sum, Kruskal-Wallis test for univariate analyses and logistic or linear regression for multivariate analyses. These analyses will be

performed on both the Intent-to-Treat and the Per Protocol populations. Subgroup comparisons will be considered secondary analyses and will not be adjusted.

9 **Pooling Across Centers**

To assess the validity of data pooling, heterogeneity across sites will be examined using relevant methods, such as random effect models (continuous variables), contingency tables or binary logistic regression (categorical variables), or Cox proportional hazards (event time variables). Any sites containing fewer than 10 subjects will be aggregated in this analysis.

Monitoring efforts will be allocated to assess whether sites are adhering to the protocol in a standardized manner to minimize the presence of heterogeneity across study centers.

10 Lost to Follow-Up and Missing Data

Every effort will be made to keep all missing data, particularly the 30-day outcomes, to a minimum. Some data may be missing, mainly due to lost-to-follow-up (LTFU) subjects. Subject discontinuation rates will be tabulated by the reason for early termination.

The primary analysis will be data as observed. Sensitivity analyses of the primary safety endpoint will be performed for subjects with missing primary safety endpoint at 30-day follow-up as follows:

- The subjects will be excluded from analysis
- Their primary safety outcome will be imputed using the worst clinical scenario assuming the subject experienced a primary safety event
- Their primary safety outcome will be imputed using the best clinical scenario assuming the subject did not experience a primary safety event

11 Reviewers and Core Lab

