The sample size calculation assumes that 6.1% (22/360) of the study subjects experience a primary safety event as compared to 6.1% (272/4454) of the TOTAL trial high thrombus burden subset. Based on a binomial analysis with a non-inferiority margin of 10%, a study of 360 Indigo System subjects will have 99% power with a one-sided alpha of 0.025. The sample size was adjusted to 400 subjects to account for up to 10% attrition rate.

3 Interim Analysis

No interim analyses are planned for the purpose of terminating the study for a positive result. No adjustments will be made to the confidence bounds for the final analysis. Interim analysis may be performed for purpose of regulatory submissions and/or publication of study results.

4 General Statistical Considerations

Baseline data including, but not limited to demographics, clinical characteristics, and angiographic characteristics will be summarized using descriptive statistics.

All confidence intervals presented will be two-sided. All statistical tests will be two-tailed with a significance level of 0.05. Descriptive statistics will be provided, which includes the number of observations, mean, median, standard deviation, minimum and maximum for continuous variables and counts and percentages for discrete variables. Analyses will be conducted using SAS (SAS Institute, Cary, NC).

Results collected at multiple visits will be summarized at each visit for which they are collected as described under Schedule of Assessments Table 2 in CHEETAH study protocol version at the time of database lock. Summaries for all measures will include all observed data for each visit. See Section 10 in SAP for lost to follow-up and missing data.

5 Definition of Populations

The number of subjects for each of the following categories will be summarized for final analysis:

• Screened:

Screened patients are all patients considered for participation in the study, whether or not they sign informed consent.

• Screen Failure:

Screen failure patients are all patients considered for participation in the study, who failed to meet inclusion criteria or met exclusion criteria. These patients may or may not have signed an informed consent form. Screen failure patients with their reasons for screen failure will be summarized.

• Enrolled:

Enrolled subjects are all subjects in which the Indigo CAT RX Aspiration Catheter enters the body and informed consent is obtained (whichever is later).

• Completed:

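### SAP section 8 tests the effect of age through a single cut at 65 years; if risk changes smoothly with age, this gives up over a third of the age information and some power, at no risk to the primary conclusion

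*Combined protocol and SAP*

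**What the plan says.** SAP section 8 sets out its purpose and scope: "To evaluate the impact of baseline condition on outcomes, subgroup analyses will be performed for the primary endpoints and secondary safety variables". It then fixes the variables: "The subgroups below will be used for these analyses". For age the list has two levels, below 65 years and 65 years or older. No reason is given for the cut, and no analysis of age as recorded is described.

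The methods are named together: "Fisher's exact test, Wilcoxon rank sum, Kruskal-Wallis test for univariate analyses and logistic or linear regression for multivariate analyses". The section does not assign tests to variables or say in what form age enters the regression. On status it says: "Subgroup comparisons will be considered secondary analyses and will not be adjusted".

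SAP section 4 sets the level: "All statistical tests will be two-tailed with a significance level of 0.05". SAP section 2 gives the expected yield: "The sample size calculation assumes that 6.1% (22/360) of the study subjects experience a primary safety event". Neither document states a power for any subgroup comparison.

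**The concern.** The stated aim is to learn how a baseline characteristic affects outcome. A single cut treats a 40-year-old and a 64-year-old as the same risk, and a 64-year-old and a 66-year-old as different. With about 22 primary events expected, there is little information to spare.

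At stake is a secondary result. A null row for the two age groups could be misread as showing no age effect when the same data, analysed by age as recorded, would have shown a gradient. Protocol section 1.4 expects the results to help plan later aspiration studies, so a missed gradient could carry forward. If the 65-year indicator were also used in the multivariate model, some age confounding could remain in the sex, NYHA and STEMI/NSTEMI comparisons. That part has not been quantified.

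**Working it through.** **Inputs from the documents.** 360 evaluable subjects and a 6.1% event rate (SAP section 2); two-sided 0.05 (SAP section 4); cut at 65 (SAP section 8). Protocol section 1.1 gives an average age at first MI of 65.6 years for men and 72.0 for women, which is background and not a forecast for this sample.

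**Assumed, because the documents do not give them.** Normally distributed age with SD 12; mean 62, 65.6 or 68; log-odds linear in age, with odds ratio (OR) 1.3-2.0 per decade.

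**The plan's own figures.** 22/360 = 6.1%, and 360/(1 - 0.10) = 400. An exact binomial test against 16% rejects at 43 or fewer events in 360 (one-sided alpha 0.0185) and has power above 99.99% at 6.1%, consistent with the stated 99%. That is the primary test and says nothing about age.

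**Information kept by the cut.** With c = (65 - mean)/SD and q = the share aged 65 or over, the fraction of linear information retained is φ(c)²/[q(1 - q)].

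- Mean 62: c = 3/12 = 0.25, q = 0.401, retained 0.622.
- Mean 65.6: c = -0.6/12 = -0.05, q = 0.520, retained about 0.636.
- Mean 68: c = -0.25, q = 0.599, retained 0.622.

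The loss is therefore about 36-38%. As a rough guide, 0.62 × 22 ≈ 14: the cut leaves about what 14 events would give with age as recorded.

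**Power.** Simulation with 360 subjects and 6.1% events; ranges are over the three means, and the gap is taken from the ends of the ranges.

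| OR per decade | Fisher at 65 | Continuous age | Gap (points) |
|---|---|---|---|
| 1.3 | 15-17% | 28-29% | 28-17 = 11 to 29-15 = 14 |
| 1.5 | 32-38% | 59% | 59-38 = 21 to 59-32 = 27 |
| 1.75 | 53-61% | 83-84% | 83-61 = 22 to 84-53 = 31 |
| 2.0 | 71-82% | 94-96% | 94-82 = 12 to 96-71 = 25 |

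At OR 1.5 per decade the planned test misses the gradient about two times in three (100 - 38 = 62% to 100 - 32 = 68%). Continuous age misses it about two times in five (100 - 59 = 41%).

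**Separating the cut from Fisher's conservatism.** A chi-square test on the same cut still loses about 8-26 points against continuous age. One cell from a separate 3,000-replicate run of the same scenarios shows the split. At mean 68 and OR 1.75, power is 52.5% for Fisher, 56.4% for chi-square and 82.4% for continuous age. The total gap is 29.9 points: 26.0 from the cut and 3.9 from Fisher. With no age effect, continuous age rejected in 3.8-5.6% of replicates across runs, so the gain is not bought with materially more false positives.

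**Where the range does not apply.** Further runs used OR per SD, where OR per decade = (OR per SD)^(10/12).

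- Weak effect, OR per SD 1.2 (1.2^(10/12) = 1.16 per decade): loss about 4 points at mean 60 or 65.
- Very strong effect, OR per SD 3.0 (2.5 per decade): loss about 4-7 points at the same means.
- Older sample, mean 74 and OR per SD 1.5-2.0: loss about 33-55 points.
- True step at 65: the planned cut wins. At mean 60 and step OR 1.5-4, Fisher gains about 2-15 points over linear age. At mean 65.6 and step OR 3, power is 58% for Fisher and 44% for continuous age.

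**The case against.** The strongest reply is that nothing in the study turns on this. The primary test compares one proportion with 16% and is unadjusted; subgroup comparisons are labelled secondary. In a single-arm study the age comparison is prognostic, not an interaction with treatment. Age groups are a legitimate reporting choice, and citing no guideline for the cut is not an error. All of that stands, and it limits the weight of the point.

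It is also fair that the size cannot be derived from the documents, that a smooth gradient favours continuous age by construction, and that a cut at 65 is close to its most efficient position if the mean age is near 65.6. These are reasons to state the range with its assumptions. They do not supply the missing continuous analysis.

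Three stronger readings are tempting and are not supported:

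- **That the cut throws away most of the age information.** At means of 62-68 it keeps about 62-64%.
- **That age is examined by Fisher's exact test alone.** The same sentence of SAP section 8 names rank tests and regression. Fisher's test is simply the listed univariate test that fits a yes/no endpoint in two groups.
- **That the regression is certain to use the 65-year indicator.** The statement that the listed subgroups will be used points that way, but the form of age in the model is not given.

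Protocol section 10.12 plans an adjusted analysis with key baseline variables. Its purpose is to look for site effects, and it names neither age nor its form, so it does not close the gap.

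**Conclusion.** The point holds as a low-cost improvement to a secondary analysis. As written, SAP section 8 evaluates age through one cut at 65 and specifies no continuous term. If risk changes smoothly with age, that discards about 36-38% of the linear information. It costs about 11-31 points of power, of which about 8-26 come from the cut itself.

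Those power figures rest on an assumed age SD of 12, mean of 62-68 and OR of 1.3-2.0 per decade, with 360 subjects and about 22 events. A reader might take the range as a fixed property of the plan. It is not: the loss is smaller for weak or very strong effects, larger in an older sample, and reversed for a true step at 65. Nor does the point touch the primary conclusion.

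**What to change.** In SAP section 8:

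1. Keep the under-65 and 65-and-over rows, labelled as descriptive.
2. State that the test of age uses age as recorded. Either fit a one-term logistic regression reporting the odds ratio per 10 years with its 95% confidence interval, or use the Wilcoxon rank sum test, which the section already names, to compare age between subjects with and without the event. Over OR 1.3-2.0 the Wilcoxon version had power of 27-94%, against 29-95% for continuous age in the same run.
3. State that age enters the planned multivariate regression as one continuous term.

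The cost is a sentence or two of text. It needs no new data, subjects or procedures, and a continuous term uses the same single degree of freedom as the indicator. The downsides are that the logistic version assumes linearity in the log-odds, which the rank test avoids, and that continuous age has less power if the true effect is a step at 65. The retained descriptive rows would still display such a step.

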11.1 Independent Medical Reviewer (IMR)

The Independent Medical Reviewer will review and adjudicate safety events based on criteria established in the IMR charter.

3.0		 Section 7.3 Analysis of Adverse Events: included definition of procedure and device related events inadvertently not reflected in version 2.0
4.0		 Section 2: reordered text to match the protocol verbatim Section 7.3: added MedDRA analysis for all cause of death, additional summary of nonserious AE Section 8: added diagnosis subgroup analysis
